10.0 STUDY CALENDAR

Required Studies	Month 0 (Pre-Study)	Study Start	Month 3 (± 14 days)	Month 6 (± 30 days)	Month 9 (± 14 days)	Month 12 (± 14 days)	Month 15 (± 14 days)	Month 18 [10] (± 30 days)	Month 21 (± 14 days)	Month 24 (± 30 days)
PATIENT EVALUATIONS										
Consent & Enrollment [14]	X									
Patient information [1]	X									
History & Physical [13]	X		X	X	X	X	X	X	X	X
Pill Diary [2]		X	X	X	X	X	X	X		X
Toxicity Notation		X	X	X	X	X	X	X	X	X
Laboratory tests [3]	X		X	X	X	X	X	X		X
Pregnancy Test [12]	X									
Audiometry [4]	X							X		
DIAGNOSTIC EVALUATIONS										
Endoscopy [5]	X			X				X		X
Histology assessment	X			X				X		X
H. pylori status [11]	X			X				X		X
INTERVENTIONS										
Dispense study drug [6]		X	X	X	X	X	X			
Adherence assess [7]			X	X	X	X	X	X		
H. pylori treatment [8]				X						(X) [9]

Study Calendar notes:

1. The subject assessment at enrollment includes demographic information and risk factor assessment.
2. While participant is on the protocol intervention, the pill diary is reviewed at each visit.
3. The laboratory tests include CBC (Hgb, Hematocrit, WBC, platelets), liver tests (bilirubin, AST, ALT) and creatinine.
4. Audiometry is performed at the pre-study visit (after all eligibility criteria are met), and at 18 months. Patients are screened for hearing impairment at each study visit, and referred for audiometry, if indicated.
5. Endoscopy with gastric biopsy mapping for histology assessment is the standard of care. The index endoscopy is performed for clinical indications. Samples obtained at the time of the index endoscopy per SOC and prior to patient consent for this study may be submitted for research once informed consent is obtained. The Month 24 endoscopy is considered a surveillance endoscopy in patients with precancerous lesions.[61] The allowable timeframe for each follow-up endoscopy is – 30/+60 days.
6. A three-month supply is dispensed on Day 1 and every 3 months through Month 15. Patients will dose for a total of 18 months and then be followed for an additional 6 months.
7. The adherence assessment consists of the pill count. Phone contact (weekly in months 0-6; monthly in months 6-18) is planned with the patients for adherence assessment, and is performed at the discretion of the study centers.
8. *H. pylori* treatment consists of the standard antibiotic regimen, per usual standard of care. Patients who are *H. pylori* positive at study enrollment are offered therapy at Month 6. (Section 6.0).
9. If a patient is *H. pylori* positive at 24 months, they will be offered additional treatment through their local providers. This intervention is outside of the scope of the study.
10. If the patient terminates the protocol intervention between completion of Month 3 and Month 18, the complete physical exam, blood draw (CBC, chemistries), pure tone audiogram, and endoscopy will be offered to the patient at that time. If the patient terminates the protocol intervention prior to Month 3, the physical exam, blood draw (CBC, chemistries), and pure tone audiogram are recommended, without endoscopy. Endoscopy will be offered to all patients at Month 24 as part of the clinical surveillance protocol (usual care) at the sites for subjects with premalignant lesions.
11. *H. pylori* infection diagnostic evaluations. Active *H. pylori* infection status (positive or negative) is assessed by gastric histology and stool antigen testing at the time of each endoscopy. In addition, *H. pylori* antibody ELISA testing is performed at the first endoscopy only, for assessment of ever-infected status.
12. Pregnancy testing (serum or urine) is required for all women of childbearing potential (WOCBP) within 14 days prior to the first dose of study drug. WOCBP of childbearing potential are defined as those not surgically sterile or not post-menopausal (i.e. if a female patient has not had a bilateral tubal ligation, a bilateral oophorectomy, or a complete hysterectomy; or has not been amenorrheic for 12 months in the absence of an alternative medical cause, then patient will be considered a female of childbearing potential). Postmenopausal status in females under 55 years of age should be confirmed with a serum follicle-stimulating hormone (FSH) level within laboratory reference range for postmenopausal women.
13. Each physical exam should include assessment of vital signs.
14. Consent should be obtained within 60 days prior to the start of study treatment.

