Pregnancy and Lactation: Eflornithine is contraindicated in women who are or may become pregnant and in nursing mothers. It is likely that eflornithine will cause fetal harm when administered to pregnant women. Eflornithine has been shown to have a contragestational effect in mice, rats, and rabbits, when given in doses equivalent to approximately fifty-times the dose used in human chemoprevention trials. If this drug is used during pregnancy, or if the patient becomes pregnant while taking this drug, the patient should be apprised of the potential hazard to the fetus. Eflornithine is also contraindicated in patients who are hypersensitive to eflornithine or any of the inactive ingredients.

c. PHARMACOLOGY

Kinetics: Therapeutic drug concentration is not established. Time to peak concentration for oral eflornithine is 4-6 hours. Absorption: for the oral solution is 54-58% and is unaffected by feeding status. Distribution: no protein binding sites, crosses blood-brain barrier. Volume of distribution is 0.3-0.35 liters/kg.

Metabolism: urinary recovery of unchanged drug as eflornithine is 86% and essentially not metabolized. Excretion: renal excretion. Elimination half-life: 3-3.5 hours but once daily dosing is sufficient to maintain efficacy.

Formulation: Eflornithine 250 mg and placebo are supplied as tablets.

Composition of Eflornithine: The active compound is DFMO (as the monohydrate monohydrochloride monohydrate) (Eflornithine HCl) 250 mg; with microcrystalline cellulose, starch 1500, silicon dioxide, magnesium stearate and opadry.

Composition of Eflornithine placebo: Dibasic calcium phosphate dihydrate, microcrystalline cellulose, starch 1500, hypromellose, silicon dioxide, magnesium stearate, opadry (yellow).

Storage and Stability: Tablets are stored at room temperature.

Administration: Two tablets by mouth daily taken with food. The tablets are a light tan color.

Supplier: Eflornithine and placebo will be supplied by Cancer Prevention Pharmaceuticals, Tucson, AZ, USA.

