 - a. Blood counts: WBC \geq 4.0 /mcl, platelets \geq 100,000 /mcl and hemoglobin \geq 11.0 g/dL
 - b. Kidney function: Creatinine $<$ 1.6 x IULN (institutional upper limit of normal)
 - c. Liver function tests: Bilirubin \leq 2.0 mg/dL and AST (SGOT) or ALT (SGPT) \leq 2 x IULN
11. Patients must not be pregnant or nursing (due to eflornithine pregnancy class C). Women and men of reproductive potential must have agreed to use an effective contraceptive method.

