8.2 Study Intervention Schedule

Agent	Dose	Route	Interval
Eflornithine placebo	2 tablets	Oral	Daily for 18 months
Or			
Eflornithine*	2 tablets	Oral	Daily for 18 months

*Each eflornithine tablet is 250mg

Initial Visit (pre-randomization): Patient should have history and physical, weight, and blood draw (include CBC: Hgb, hematocrit, WBC, platelets; liver tests: bilirubin, AST, ALT; and creatinine). Additionally, women of child bearing potential will have a pregnancy test (serum or urine) within 14 days prior to start of study drug. Patients will be evaluated via endoscopy at baseline. Audiometry testing to document air conduction will be conducted.

Follow-up during intervention (Months 0-18): During the 18 month intervention, patients will be followed at three month intervals with clinic visits which include a physical exam and blood draw (CBC, chemistries). Endoscopic surveillance is incorporated into the follow up at 6 and 18 months. Study drug dispensation coincides with clinic visits. More frequent patient contact is planned (e.g., phone follow-up: weekly in months 0-6, and monthly thereafter), at the discretion of the site investigator, in consultation with the study PIs, as in prior clinical trials.[59,60]

Final intervention visit (Month 18): At Month 18, all patients will have a complete physical exam, blood draw (CBC, chemistries), and pure tone audiogram.

Post intervention follow-up (Month 24): All patients will be followed for 6 months after completion of the 18 months of intervention off of study medications.

Patient removal from protocol: If the patient terminates the protocol intervention between completion of Month 3 and Month 18, the complete physical exam, blood draw (CBC, chemistries), pure tone audiogram, and endoscopy will be

offered to the patient at that time. If the patient terminates the protocol intervention prior to Month 3, the physical exam, blood draw (CBC, chemistries), and pure tone audiogram are recommended, without endoscopy. Endoscopy will be offered to the patient at Month 24 as part of usual care and clinical surveillance protocol at the sites for subjects with premalignant lesions.

8.3 Endoscopy Procedures (Months 0, 6, 18, 24):

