8.6 Study Blinding Information and Criteria for Removal from Protocol Treatment

- a. All patients, study centers, pathology and laboratory personnel will be blinded to study treatment. The study pharmacist at each study site is unblinded to facilitate randomization.
- b. Laboratory and pathology specimens will be labeled by patient identification number and initials only.
- c. The study drug may be discontinued without unblinding the patient. Patient's treatment will be unblinded only if the treating physician demonstrates a compelling medical need for this information (Appendix).
- d. As study arms will be analyzed using an intent-to-treat method, patients are never "dropped" from the study.

- e. Patients will be removed from protocol treatment under the following circumstances, and all reasons for discontinuation will be documented:
 - Unacceptable toxicity (Section 8.0).
 - A patient who becomes pregnant or declines contraception.
 - Intercurrent illness which would affect assessments, in the opinion of the treating physician.
 - Cumulative delay of study intervention >90 days for any reason.
 - The patient may withdraw from the study at any time for any reason.

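### Eflornithine is described as likely to harm a fetus, yet the only scheduled pregnancy test precedes the first dose, and the five later three-month supplies are dispensed without one

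*Combined protocol and SAP*

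**What the plan says.** Section 3.1 contraindicates eflornithine in women who are pregnant or might become so, and states: "It is likely that eflornithine will cause fetal harm when administered to pregnant women". The animal finding it cites arose "when given in doses equivalent to approximately fifty-times the dose used in human chemoprevention trials".

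The safeguards around this are as follows.

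- **Entry.** Section 5.2, item 11 excludes pregnant and nursing women and adds: "Women and men of reproductive potential must have agreed to use an effective contraceptive method".
- **Removal.** Section 8.6e lists among the grounds for stopping protocol treatment: "A patient who becomes pregnant or declines contraception".
- **Testing.** Study Calendar note 12 reads: "Pregnancy testing (serum or urine) is required for all women of childbearing potential (WOCBP) within 14 days prior to the first dose". Section 8.2 says the same for the initial visit: "women of child bearing potential will have a pregnancy test (serum or urine) within 14 days prior to start of study drug". The pregnancy-test row of the calendar has one mark, at Month 0.
- **Visits and supply.** In section 8.2, during treatment, "patients will be followed at three month intervals with clinic visits which include a physical exam and blood draw", and "Study drug dispensation coincides with clinic visits". Calendar note 6 puts dispensing on Day 1 and then three-monthly up to Month 15. Calendar note 3 limits the laboratory panel to blood counts, liver tests and creatinine.
- **After a pregnancy is known.** Section 15.6 requires reporting within 24 hours of site awareness, and section 17.3 lists exposure of a pregnant woman as a possible reason for unblinding.

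**The concern.** The removal rule in section 8.6e can act only if the pregnancy is known, and nothing scheduled after the first dose is designed to detect one. A site that follows the calendar exactly can give a woman with an unrecognised pregnancy a further three months of study drug at a visit where she is examined and has blood drawn. By the protocol's own rule she should have stopped.

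The schedule is also uneven. Blood counts, liver tests and creatinine are repeated at every resupply visit, and calendar note 4 asks for hearing to be screened at each study visit. The hazard that section 3.1 calls likely has no scheduled check during treatment. Note 12 defines childbearing potential in detail, including hormone confirmation of menopause in women under 55, so the plan expects such women among participants aged 30 to 69.

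What is at stake is participant and fetal safety.

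**Working it through.** The plan states no figure of its own to reproduce. The check is a count from the Study Calendar and its notes.

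**Supplies and tests for one woman of childbearing potential**

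| Dispensing | Months covered | Scheduled pregnancy test beforehand |
|---|---|---|
| Day 1 | 0–3 | Yes (within the preceding 14 days) |
| Month 3 | 3–6 | No |
| Month 6 | 6–9 | No |
| Month 9 | 9–12 | No |
| Month 12 | 12–15 | No |
| Month 15 | 15–18 | No |

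- Supplies: 6. Supplies preceded by a scheduled test: 1. Supplies without one: 6 − 1 = 5.
- Dosing time covered by those five: 5 × 3 = 15 of 18 months, and 15/18 = 83%.

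**What one test could avert**

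One supply lasts three months, about 91 days. At two tablets a day (section 8.2) that is 91 × 2 = 182 tablets. This is a ceiling. It is reached only if the pregnancy would otherwise have gone unrecognised, with dosing continuing, for the whole of the next supply.

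**Effect of testing at each re-dispensing**

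Scheduled tests per woman rise from 1 to 1 + 5 = 6. The longest planned stretch on drug without a test falls from about 18 months to about 3.

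**Number of added tests trial-wide**

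The accrual table in section 2.0 targets 150 women. The share of childbearing potential is not given, so 25% to 75% is assumed.

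- Women concerned: 0.25 × 150 = 37.5 to 0.75 × 150 = 112.5.
- All complete dosing: 37.5 × 5 = 187.5 to 112.5 × 5 = 562.5, about 188 to 563 tests.
- If the 10% dropout in section 12.2 all occurs before Month 3: 187.5 × 0.9 = 168.75 to 562.5 × 0.9 = 506.25, about 169 to 506 tests.

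The assumed share enters only this cost range, not the 5-of-6 count.

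**Whether another procedure fills the gap**

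- The contraception agreement at entry, and removal of a patient who declines contraception, lower the chance of pregnancy but do not detect contraceptive failure.
- History, physical examination and toxicity notation occur at each resupply visit, but no pregnancy question or test is specified. Section 3.1 lists nausea (6.5%) and, at 1–2%, vomiting and menstrual disorders as drug effects, so signs that might suggest pregnancy could be recorded as toxicity.
- Planned phone contact (section 8.2 and calendar note 7) is at the site's discretion, and note 7 gives its purpose as adherence.
- Sections 15.6 and 17.3 begin only once a pregnancy is known.

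**The case against.** The strongest defence is that this is a coherent, lighter scheme rather than a contradiction. It combines a baseline test, required contraception, removal on pregnancy or on declining contraception, three-monthly clinical review and 24-hour reporting. A removal rule does not in itself imply scheduled testing, since section 8.6e also removes patients for intercurrent illness or toxicity as these come to light. Section 8.1 tells patients they may call or visit at any time, and section 8.2 plans phone contact weekly in the first six months and monthly thereafter. The risk may be smaller than section 3.1 suggests, because the animal effect was at about fifty times the chemoprevention dose and section 5.2, item 11 gives the drug as pregnancy class C. With 150 patients per arm, half receive placebo. The consent form and Investigator's Brochure were not reviewed and may contain instructions on contraception or self-testing.

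Much of this stands as context. Expected exposure to active drug is about half what a count of supplies suggests, the 83% is a share of supplies rather than a risk, and no document fixes a testing interval. None of it detects an unrecognised pregnancy before resupply. The blind means that the stopping rule covers every supply. Despite the dose multiple and the class C label, section 3.1 still contraindicates the drug and section 8.6e still requires stopping.

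A practical objection also stands in part. The documents give no turnaround time for a serum test. If the result is not available the same day, drug would be delayed or a return visit needed. A point-of-care urine test avoids this.

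**Conclusion.** The concern holds. The protocol schedules one pregnancy test, before the first dose, and none before the five later supplies, which cover 15 of 18 dosing months. The count is certain on the text of the calendar, note 12 and section 8.2, and no on-treatment pregnancy test was found elsewhere in the protocol. The claim extends only to tests scheduled there, because the consent form and Investigator's Brochure were not available.

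The benefit per detected pregnancy is at most one supply averted, about 91 days or 182 tablets, which would be placebo for about half the women. How often this would happen cannot be estimated. The case for change rests on the protocol's own description of the hazard, its own stopping rule and the low cost of testing. The primary endpoint, power and analysis are not affected.

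**What to change.** Amend the pregnancy-test row of the Study Calendar, note 12 and section 8.2 to require a urine or serum pregnancy test for every woman of childbearing potential before re-dispensing at Months 3, 6, 9, 12 and 15. The result should be known before drug is handed over, and drug withheld if it is positive. Urine testing at the visit is the practical choice. A Month 18 test is optional: nothing is dispensed then, so it would serve only to identify late exposure.

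The cost is five low-cost tests per woman, about 188 to 563 across the trial under the assumed 25–75% share (169 to 506 with early dropout), and staff time to run and record them. There would also be a short hold on drug while any false positive is confirmed. Dispensing already takes place at clinic visits with a blood draw, so no new visit or invasive procedure is needed if the result is available the same day. Testing shortens exposure; it does not prevent exposure between visits, so the contraception requirement remains the main protection.

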11.0 CRITERIA FOR EVALUATION AND ENDPOINT DEFINITIONS

Primary Objective

11.1 The difference in cell DNA damage between patients treated with DFMO and patients treated with placebo at 6 months. The cell DNA damage is measured using the percent positive gastric epithelial cells assessed by IHC for gamma H2AX. The mean difference between the two groups at 6 months will be calculated, accounting for their baseline measurements.

Secondary Objectives

11.2 The difference in cell DNA damage between patients treated with DFMO and patients treated with placebo for 18 months, and then followed for an additional 6 months. The cell DNA damage is measured using the percent positive gastric epithelial cells assessed by IHC for gamma H2AX. The mean difference between the two groups at 18 and 24 months will be calculated, accounting for their baseline measurements. The additional measure of DNA damage, gamma H2AX by IHC and by flow cytometry will also be assessed at 0, 6, 18, and 24 months.

11.3 The differences in the gastritis histopathology score between patients treated with DFMO and patients treated with placebo for a total of 18 months, and followed for an additional 6 months. The gastritis histopathology score is measured with a quantitative scale 0.0-6.0, for atrophy, intestinal metaplasia, and dysplasia. The mean differences between the two groups at 6, 18, and 24 months will be calculated using mixed models, accounting for their baseline measurements.

11.4 Number of patients with quantitative toxicities. Toxicities will be assessed per CTCAE criteria, and each toxicity will be assigned an adverse event (AE) term according to CTCAE definitions (each AE term = unique representation of a specific event used for medical documentation and scientific analyses), and graded as defined by CTCAE (grade 1 = mild; grade 2 = moderate; grade 3 = severe or significant but not immediately life-threatening; grade 4 = life-threatening; grade 5 = death).

10.5 To evaluate whether candidate single nucleotide polymorphisms (SNPs) relevant to eflornithine (DFMO) efficacy.

12.0 STATISTICAL CONSIDERATIONS

12.1 Data Analyses for the primary and secondary endpoints

We hypothesize that high risk subjects with precancerous gastric lesions will benefit from eflornithine, by reducing DNA damage, inflammation, and bacterial virulence, leading to attenuated histopathology and cancer risk. The primary objective is to assess whether eflornithine affects gastric epithelial cell DNA damage, measured at the 6 month time point, as assessed by percent positive cells in each patient, measured by IHC for gamma H2AX. We expect 150 patients in each group (eflornithine vs. placebo). We expect 100 patients in each *H. pylori* subgroup (*H. pylori* negative, *H. pylori* positive treated, *H. pylori* positive untreated [decline treatment]). We will examine the main effect of treatment and the effect modification from *H. pylori* status and treatment in a multivariate model.

We hypothesize a 50% reduction in DNA damage from baseline at the 6 and 18 months. We expect a modest reduction of eflornithine (10%) effect on DNA damage after treatment cessation (months 18-24), which nonetheless may remain statistically significant. We also expect a reduction in the histopathology score by 0.16-0.18 units at 18 months. We base these estimations on our prior published studies.[8,9] We assume a two-sided alpha of 0.05 and 80% power. For the main comparison, DFMO vs. placebo at 6 months (150 subjects each), a difference in DNA damage of $\geq 18\%$ (IHC for gamma H2AX) is hypothesized. A difference of ≥ 0.1 units in histopathology score at 18 months is expected.

Subgroup analysis (50 subjects each) at 6 months, where the comparator is *H. pylori* negative may detect a difference of $\geq 36\%$ and $\geq 31\%$ in DNA damage, respectively, and may detect at 18 months a difference of ≥ 0.15 units in histopathology score for both comparisons. These calculations assume normally distributed endpoints and use standard deviations from our prior work. The size of differences chosen for computations has been reduced to allow a 10% loss to follow up.

Generalized linear models with a Gaussian link are used to analyze difference in means of DNA damage (flow cytometry, immunostaining), and histopathology at 18 months. The primary endpoint will be reported in terms of marginal means and their difference (DFMO/placebo) with 95% confidence intervals (95%CI) adjusted for baseline variables (age, gender, etc.) and baseline dependent variable values. Mixed models will be used to analyze secondary endpoints including the longitudinal changes from baseline to 6, 18, and 24 months. Time between measurements will be included in the model so that random slopes for the dependent variable at each point in time and random intercepts for each subject will be initially assumed. Adjusted marginal means and 95%CI will be reported with significance levels. The subgroup analysis will involve entering the subgroup analysis variable into generalized linear mixed models: Negative *H. pylori* status, *H. pylori* positive and treated, and *H. pylori* positive and refused treatment. Marginal means and 95%CI are reported for each subgroup after adjusting for baseline variables and including the main independent variable (treatment). A main effects model and an interaction model will be assessed for the treatment and subgroup variables. Prior experience with all three measurements has shown them to be normally distributed. Comparisons of AEs and SAEs between each of the treatment groups will also be performed using person-times poisson rates, with rates being reported using exact 95% confidence intervals. Lastly, we will examine the interaction of treatment arm and genotype expression with respect to different outcomes. STATA 13 is used for computations.

12.2 Accrual Monitoring. The historical experience for patient recruitment is approximately 150 patients per year. The estimated 10% dropout rate is based on prior studies, with excellent 1-year follow-up of >93% at these same study sites.[59,60] The general populations are keenly aware of the impact of gastric cancer in their regions, and the need for prevention. We anticipate balanced recruitment between the two study sites, 150 subjects per site, but with a flexible recruitment strategy. The enrollment at each individual site will be capped at 240 (80%).

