7.0 STRATIFICATION FACTORS

Patients will be randomized to one of two treatment groups: eflornithine versus eflornithine placebo, with 150 subjects in each treatment group. A dynamic balancing algorithm will be used for randomization, with stratification by study site. *H. pylori* status is integrated into the analysis, but stratification is not performed by *H. pylori* status.

7.1 Study sites. Study enrollment will be competitive across up to three participating sites. The enrollment at each individual site will be targeted at 240 (80%), with the exception of extenuating circumstances (e.g., natural disaster, recruitment limitations, etc.).

7.2 *H. pylori* subgroups. Three subgroups of subjects with precancerous lesions will be studied as a secondary analysis, based on *H. pylori* status and acceptance of eradication treatment at enrollment: 1) *H. pylori* negative; 2) *H. pylori* positive, decline antibiotic treatment (50%); and 3) *H. pylori* positive, accept antibiotic treatment (50%). Historically, given the high prevalence of *H. pylori* infection and the natural history of reinfection, about 50% of subjects decline or accept antibiotic eradication, respectively. Thus, these 3 subgroups are common clinically we expect a *balanced distribution* at our study sites (see study schema). In summary, we expect 150 subjects in each treatment group (eflornithine, placebo) and 100 subjects enrolled in each *H. pylori* subgroup.

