7.3 *H. pylori* eradication. The secondary intervention is *H. pylori* treatment of subjects of the subgroup who are *H. pylori* positive and desire treatment, per usual standard of care. Subjects are treated with standard triple therapy (clarithromycin 500 mg, amoxicillin 1000 mg, lansoprazole 30 mg) twice daily for 14 days. This is the optimal regimen in Latin America, based on RCT results.[59] Patients are permitted to choose alternative *H. pylori* eradication regimen, per usual standard of care, in consultation with the site investigator. Patients will be treated at the 6 month time point. This *H. pylori* eradication treatment timing permits the maximum number of study subjects on DFMO monotherapy for the 6 month primary endpoint. This timing is ethical given the lifelong infection with *H. pylori* in >80% of our populations, the natural history of reinfection, and the limited short term benefit of *H. pylori* eradication for subjects with premalignant lesions. Subjects who elect to change their decision on *H. pylori* treatment during the initial 6 month period are permitted to do so. In addition, we expect infection recurrence rates of 8% in Honduras at the 18 month point based upon our Latin America RCT. If infected at 24 months, subjects will be offered treatment per local standards of care and outside of this protocol. [59,60]

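### At 6 months the two H. pylori positive subgroups have, by schedule, not yet differed in eradication, so they are better pooled there; the 18- and 24-month subgroups need section 7.2's enrollment definition

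*Combined protocol and SAP*

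**What the plan says.** All references are to the combined protocol and SAP.

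- **Subgroup definition.** Section 7.2 bases the three subgroups on H. pylori "status and acceptance of eradication treatment at enrollment": negative, positive and declining, positive and accepting. It expects 150 subjects per arm "and 100 subjects enrolled in each" subgroup.
- **Eradication timing.** Section 7.3 states "Patients will be treated at the 6 month time point", and gives the reason: the "eradication treatment timing permits the maximum number of study subjects on DFMO monotherapy for the 6 month primary endpoint". Calendar note 8 (section 10.0) says that those "positive at study enrollment are offered therapy at Month 6". Section 7.3 also lets subjects change their decision during the first 6 months.
- **Subgroup analysis.** Section 12.1 names the groups as negative, positive treated, and "positive untreated [decline treatment]). We will examine the main effect of treatment". It then gives a "Subgroup analysis (50 subjects each) at 6 months, where the comparator is" the H. pylori negative group, with detectable differences of 36% and 31% in DNA damage. At 18 months it gives 0.15 histopathology units for both comparisons. Later in 12.1 the model variable has the levels negative, positive and treated, and positive and refused. Marginal means with 95% intervals are planned for each subgroup, along with an interaction model.
- **Inputs to the sizes.** Section 12.1 uses two-sided alpha 0.05, 80% power and SDs from prior work that are not stated. It says the sizes already allow for 10% loss.

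**The concern.** There are two linked problems.

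First, a treated-versus-untreated split of the positives at 6 months falls at or before the point when eradication is given. On the planned schedule neither positive group has had it by then. The split divides the positives by stated willingness, cannot show an eradication effect, and gives up precision for the question the 6-month biopsy can answer: whether the DFMO effect depends on baseline H. pylori status.

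Second, the subgroup variable is open to more than one coding. Section 7.2 fixes it at enrollment. The word *treated* in 12.1 could be coded from treatment received or from a later decision. Either would define the groups after randomised treatment has started, so the DFMO-versus-placebo comparison within a subgroup at 18 or 24 months would no longer be protected by randomisation. Blinding (section 8.6) limits this but does not remove it, since symptoms on study drug could still influence the choice. A positive subject who accepted at enrollment and left before Month 6 has a category under 7.2 but fits neither positive label in 12.1.

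**Working it through.** **1. The plan's own sizes.** The SD is not given, so 36% and 31% cannot be rebuilt from stated inputs. They can be back-solved and compared. The formula is: detectable difference = SD × 2.8016 × sqrt(1/n1 + 1/n2), where 2.8016 = 1.960 + 0.842.

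- 18% at 150 v 150 (main comparison): SD = 18 / (2.8016 × sqrt(2/150)) = 55.6
- 31% at 50 v 50: SD = 31 / (2.8016 × sqrt(2/50)) = 55.3
- 36% at 50 v 50: SD = 36 / (2.8016 × sqrt(2/50)) = 64.2

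Equivalently, 18% × sqrt(3) = 31.2%, so the 31% agrees with the main comparison. The 36% needs a combined SD larger by 36/31 = 1.161. Using 135 and 45 per group (10% loss) leaves this ratio unchanged.

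If both comparisons use the same negatives, 1.161 is the ratio of sqrt(SD_pos² + SD_neg²), not of the two positive SDs. If, for example, the negatives' SD equals the smaller positive SD, the positive SDs are in the ratio sqrt(2 × 1.161² − 1) = 1.30. The plan explains neither figure; group-specific SDs from prior work could account for both.

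**2. What pooling gains at 6 months.** Inputs: 300 subjects, two arms and three equal subgroups (7.0, 7.2), so 300/6 = 50 per arm-by-subgroup cell. A common SD is assumed. Variances are in units of SD².

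| Contrast | Split | Pooled | SE ratio | SE cut |
|---|---|---|---|---|
| Positive v negative | 1/50 + 1/50 = 0.04 | 1/100 + 1/50 = 0.03 | sqrt(0.03/0.04) = 0.866 | 13% |
| DFMO-by-status interaction | 2/50 + 2/50 = 0.08 | 2/100 + 2/50 = 0.06 | sqrt(0.06/0.08) = 0.866 | 13% |
| DFMO v placebo within positives | 2/50 = 0.04 | 2/100 = 0.02 | sqrt(0.02/0.04) = 0.707 | 29% |

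The first row matches the comparison quoted from 12.1. The third is a different contrast, covered by the planned subgroup and interaction models. With 45 and 90 per cell the ratios are the same. For illustration only, at the back-solved SD of 55.6 the first row moves the detectable difference from 31.2% to 55.6 × 2.8016 × sqrt(0.03) = 27.0%.

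**3. Sensitivity to the subgroup sizes.**

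- Negatives 20% of enrolment (30, 60, 60 per arm): interaction ratio sqrt((2/30 + 2/120) / (2/30 + 2/60)) = 0.913, a 9% cut.
- Negatives 10% (15, 67.5, 67.5 per arm): sqrt((2/15 + 2/135) / (2/15 + 2/67.5)) = 0.953, a 5% cut.
- In both cases positive versus negative changes by the same ratio, and the 29% within positives is unchanged.
- Positives split 30:70 with one third negative: within positives the cut is 1 − sqrt(0.7) = 16% against the larger group and 1 − sqrt(0.3) = 45% against the smaller. For the interaction it is 1 − sqrt(0.06 / (2/50 + 2/70)) = 6% and 1 − sqrt(0.06 / (2/50 + 2/30)) = 25%.

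The 20% and 10% shares are assumptions. Section 7.3 cites infection above 80% in the source populations. Section 5.1 cites 90% with H. pylori-associated pathology among patients coming to endoscopy. Neither is the infection rate among eligible subjects, and section 2.0 describes loss of the organism with progression to atrophy and metaplasia.

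**4. The label, place by place.** Section 7.2 uses acceptance or refusal at enrollment. In 12.1 the list has treated and untreated, the latter glossed as declining; the model has treated and refused. Section 7.3 allows the decision to change up to Month 6. Note 8 puts the offer at Month 6 for those positive at enrollment. *Accepted at enrollment* and *treated* can therefore be different people, and no section says which coding governs.

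**The case against.** The case for leaving the plan alone has real parts.

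- **The 6-month groups are inferred.** This stands. A reader might infer that 12.1 expressly plans a treated-versus-untreated comparison at 6 months; it does not say so. The inference rests on the two sizes, the negative comparator, the three groups listed just before and the later mention of both comparisons.
- **Acceptance at enrollment is a legitimate baseline factor.** This also stands. A 6-month split by willingness is possible, its values are the pre-eradication reference for later contrasts, and a pooled contrast can be taken from the three-level model. Nothing is irrecoverably lost; the issue is which contrast is specified and sized.
- **Some subjects could have had eradication before the biopsy.** Section 7.3 speaks only of a maximum number on monotherapy. Calendar note 5 adds a window: "The allowable timeframe for each follow-up endoscopy is" from 30 days early to 60 days late. The order of biopsy and antibiotics is not stated. This allows exceptions but does not create a planned treated group.
- **Section 7.2 already governs.** This holds in part. The words for declining and refusing in 12.1 point back to the 7.2 decision, so the documents do not support reading 12.1 as plainly using treatment received. But *treated* appears twice and is not tied to 7.2.
- **The decision may already be recorded.** A reader might infer from calendar note 1 that it is not. That note explains only the patient information row, and the enrollment form is not shown, so a missing field is not established.

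**Conclusion.** The point holds in a limited form and is a cheap improvement. At 6 months, on the natural reading of 12.1, the positives are divided by a label that by schedule carries no eradication content. Pooling them cuts the standard error by about 13% for positive versus negative and for the interaction, and by 29% for DFMO versus placebo within positives. These figures rest on 50 per cell and a common SD. The 13% shrinks if negatives are fewer than the expected one third; the 29% does not.

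The two sizes at equal n need different variances. A reader might infer an arithmetic error, or that the two positive groups' SDs are in the ratio 1.16. The documents support neither, because the SDs are not shown and both comparisons share the negatives.

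For 18 and 24 months the wording leaves open a post-randomisation subgroup. A reader might infer that the DFMO estimates there will be biased. The documents do not establish that such a coding will be used, and give nothing from which to estimate a bias. The subgroup analysis is secondary. The primary DFMO-versus-placebo comparison is unaffected, and the timing of eradication is not questioned.

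**What to change.** In section 12.1:

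1. At 6 months, use baseline H. pylori status in two levels, positives pooled versus negative, for the main subgroup contrast, the DFMO effect within each level and the interaction. Replace the two 6-month sizes with one, recomputed by the sponsor from its own SD, and state the SD and the scale of the percentage. No value is proposed here because neither is given.
2. At 18 and 24 months, define the three groups by baseline status plus the acceptance decision recorded before randomisation, consistent with 7.2. Replace the *treated*, *untreated* and *refused* labels with ones that name that decision. The 6-month value stays in the mixed model as the pre-eradication measurement.
3. Reconcile 7.2, 7.3, 12.1 and calendar note 8 on when the decision is recorded. If it is not already captured before randomisation, add one field.

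The cost is wording, and at most that field. The downsides are that there is no headline three-group contrast at 6 months, and that subjects who change their decision are analysed under the original one.
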